For the quantitative survey, the main evaluation sample will consist, roughly, of half coupon winners and half non-winners. More precisely, we will interview all large coupon winners, and randomly select an equal number of small coupon winners to interview. In addition, to address the question of selection into insurance, we will oversample households that purchased insurance from the population of small coupon winners. In total, our sample of approximately 5,200 households will consist of approximately 46% large coupon winners and 54% small coupon winners. For the quantitative survey, the main evaluation sample will consist, roughly, of half coupon winners and half non-winners. More precisely, we will interview all large coupon winners, and randomly select an equal number of small coupon winners to interview. In addition, to address the question of selection into insurance, we will oversample households that purchased

insurance from the population of small coupon winners. In total, our sample of approximately 5,200 households will consist of approximately 46% large coupon winners and 54% small coupon winners¹.

The survey team will interview households between two and seven weeks after the village meeting². An Evaluation Representative will attend each village meeting to help run the Lucky Draw lottery. At the end of each village meeting the Evaluation Representative will randomly select a number of the small coupon winners to be interviewed. SKY Insurance Agents will visit these households, as well as all large coupon households, before the 21st of the month. Once all households have had the opportunity to purchase insurance, we will interview these sampled households. Table 2 offers a breakdown of the interview sample.

	Large coupon wi	inners S	Small coupo	n winners	Additional small coupon	Total
	(100% sampled)		(25% sampled) buyers		(50% sampled)	
	1	2	3	4	5	6
	Total	Buyers (est.)	Total	Buyers (est.)	(Estimated)	(Estimated)
Per meeting	9.5	3.8	9.5	0.57	1.8	20.8
Total	2,375	950	2,375	143	453	5,203

Table 2: Quantitative survey sample

Notes: We assume 250 village meetings. Based on the results from the pilot test in 2007, we assume 40% of large coupon winners purchase SKY and 6% of small coupon winners purchase SKY.

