5.1. Household Survey

The principal component of data collection is a large-scale survey collecting three rounds of quantitative data from approximately 5,200 households. The sampling is described above in section 4 of this protocol.

The baseline will be a rolling survey, administered to each village approximately two to seven weeks after the Lucky Draw is held³. The second round will use the same rolling format, and will be administered 12 months after the baseline. The final survey round will be administered 24 months after the baseline.

This survey will collect data on household demographics, wealth indicators, self-perceived and objective health measures, health care utilization and spending, assets and asset sales, savings, debt, health risk behaviors, willingness to take financial risks, trust of institutions, means of paying for large health expenses, and willingness to trade current for future income. We describe the elements of this survey in detail in Section 6, below.

The survey will ensure high quality data using multiple means. All surveys will be reviewed at the household by the enumerator. All surveys will then be reviewed by a data editor who reviews unclear responses and outliers and checks for data consistency (e.g., mothers who are male or age 7). All surveys will then be reviewed by a field supervisor. The field editor and supervisor also review a subset of questions with a subset of households to check on data quality. These checks will include all very large responses for high health care costs (an important point, as health care costs are dominated by a small number of outliers.) When data are entered, we run a further set of checks for consistency and permissible values. Unexpected answers and outliers lead to rechecking the paper questionnaires.

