To measure selection into insurance, we will run five sets of analyses. First, we will look at average baseline characteristics of households that buy SKY and compare them to those who don't buy SKY. We will also run a logistical regression to determine the impact of each indicator on the purchase of insurance (where decision to purchase (0 or 1) is on the left- hand side and household and health facility quality characteristics are on the right-hand side of the equation).

Second, we will compare characteristics and average health care utilization of households that buy SKY at different prices, to examine whether a lower price induces more risk pooling (that is, attracts a healthier applicant pool).

Third, we will use external sources of data—the Cambodia Demographic Health Survey (DHS) and 2008 Census —to compare the profiles of village members who attend SKY village meetings and of SKY members to the general population (at the national, provincial and possibly district level). In the household survey our demographic measures (household size and members' age and sex) and some of our health (e.g., body mass index, that is, weight for height) and socioeconomic status (e.g., education) data are directly comparable to the DHS.

Fourth, we will examine selection using SKY data on membership and member utilization of health facilities. To

illustrate the possibilities, in 2007 all but one of the SKY members who had used a health center at least once renewed their membership, which was a far higher renewal rate than among those who had not used a facility at least once. This is a simple analysis using incomplete data, but illustrates the potential for such data to provide important insights into who is keeping and who is dropping insurance.

Finally, the Village Monograph will give us an in-depth qualitative study of how households make the decision to purchase insurance, how they use health facilities differently when covered by it, and how they decide to renew or drop insurance—all of which help us understand selection into the insurance market.

B. Predictors of Take-up

We will use the following measures that are collected using the household survey (described above) to predict take-up of SKY insurance:

• Wealth/income indicators (e.g., a wealth index created by asset ownership)

 Demographic characteristics of the household (age of members, number of members, gender and age of head/primary decision-maker, etc.)

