• Past health utilization of family members (as discussed in previous sections)

· Past experience with large health shocks or expenditure

 Health level of family members at date of purchase (as discussed in previous sections)

• Alternate means of health financing in the absence of insurance (access to loans, etc.)

In addition, the household survey will include measures of the following constructs that may affect take-up. When feasible, we ask who in the household was influential in deciding to buy or decline SKY insurance and will pose these questions to someone who was influential. We will measure: • Perceptions of public health care quality

• Self-perceived predicted health risk/predicted need for health care for each household member

• Cautiousness with money (financial risk aversion), as measured by a series of hypothetical lottery games

• Cautiousness with health (health risk aversion), as measured by a series of questions regarding risky health behaviors

• Willingness to try new products

• Personal discount rate/preference for present consumption, as measured by a series of hypothetical games that trade present for future consumption

• Trust of institutions (government, NGOs, etc.)

We will also measure health care quality using the household survey and GRET's quality assessment, as described above. Finally, we will use village maps and data from the village leader to calculate distance from public and other health facilities.

Methodology for Objective 3: Effects of health insurance on public health facilities

We will examine several measures of public health center quality in the household survey:

• Perceptions of public health facilities (distinguishing whether the respondent has been to public facilities)

For those who have been to public facilities, reports on:

o Availability of equipment and supplies (including drugs) o Staff treatment of patients

o Staff and facility observance of official work hours

o Under-the-table payments in addition to official user fee payments

Surveys of member facilitators will provide longitudinal data on:

• Staff and facility hours (including observance of official hours)

 Completeness (and potentially, accuracy) in recordkeeping · Availability of equipment and drugs

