Qualitative research will use in-depth interviews to examine how SKY has affected health facilities. Questions will cover facility equipment, supplies, and other measures of overall functioning. In addition, staff will be asked about their salaries, hours, and thoughts on SKY. Health care providers will also be asked about the care-seeking behaviors of SKY versus non-SKY members. For example, we will ask about the number of inpatient versus outpatient visits, severity of illness at visits, and days spent in the hospital for both SKY members and non-SKY members.

We will also look at trends in the quantitative measures of health center quality (from the surveys of households and of member facilitators). SKY members may increase their expectations of health center quality once they join SKY. Thus, we will emphasize attitudes of low-coupon households. SKY membership will be fairly low in this group, so any effects of SKY membership should not bias results substantially.

Methodology for Objective 4: Contribution to the general body of knowledge

Currently, several countries around the world are considering the development of health insurance programs, yet little is known about the effects of health insurance on outcomes of interest. The evaluation of SKY will thus serve as a global public good. Rigorously documenting the program's impact-both what works and what does not-will allow Ministries of Health, donors, and policymakers around the globe to learn from SKY's example. The results of this evaluation will serve as an important tool as governments and aid organizations determine whether voluntary health insurance represents a viable strategy to meet their health goals. In this way, GRET's initial investment in health insurance in Cambodia may multiply to improve health and economic outcomes in developing countries around the world.

The following outputs will allow us to contribute to the general body of knowledge on health insurance, risk research, and development:

• Each year throughout the project, we will meet with Cambodian Ministry of Health officials and international donors to ensure that relevant questions are being answered.

• As data become available, we will produce reports on program impact and take-up of insurance.

- Reports will be produced in English and Khmer, and will be distributed to donors and Ministry of Health officials.

- Reports will also be posted online and will be publicly available.

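### Objective 2 treats attitudes and expectations collected after the purchase decision as predictors of that decision, so buyer versus non-buyer gaps in them can mix selection with effects of buying

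*Protocol*

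**What the plan says.** **Timing.** Section 4 (Sampling Strategy) sets the order. After the village meeting, "SKY Insurance Agents will visit these households, as well as all large coupon households, before the 21st of the month". Then: "Once all households have had the opportunity to purchase insurance, we will interview these sampled households". The lag is also stated: "The survey team will interview households between two and seven weeks after the village meeting". Section 5.1 calls this same interview the baseline: "The baseline will be a rolling survey, administered to each village approximately two to seven weeks after the Lucky Draw is held". Later rounds come at 12 months and then "The final survey round will be administered 24 months after the baseline". No survey round precedes the decision.

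**Use.** In Methodology for Objective 2, part A, the first selection analysis is: "we will look at average baseline characteristics of households that buy SKY and compare them to those who" do not buy. A logistic regression follows, with purchase as the outcome and household and facility characteristics as regressors; its stated purpose is to determine the impact of each. Part B lists the household-survey measures used to predict take-up, and adds constructs that may affect it: perceived quality of public care, "Self-perceived predicted health risk/predicted need for health care for each household member", financial and health risk aversion, willingness to try new products, discount rate and trust in institutions. Section 2 also names expected utilization of public facilities as a determinant. Of all these, only the household members' health level is tied to the date of purchase.

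**Reverse path.** Methodology for Objective 3 says: "SKY members may increase their expectations of health center quality once they join SKY". Its response is to emphasise low-coupon households when quality trends are examined. Objective 2 contains no counterpart.

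**The concern.** A predictor of a decision should be measured before it, or at least refer to a time before it. Here the subjective items are asked of people who already know whether they are insured, and who have been visited by an agent. A household that has bought cover at public facilities may expect to use them more because it is covered. It may also bring its stated need, or its view of the facilities, into line with the choice it has made.

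Two conclusions are exposed. Part A of Objective 2 defines adverse selection by anticipated health care cost, so predicted need and expected use bear on it directly. Perceived quality and trust bear on the causes of low take-up, from which the protocol intends to judge whether non-buyers decide reasonably and whether SKY should seek to reach them.

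**Working it through.** **1. The plan's sample figures reproduce (Section 4, Table 2).** 9.5 × 250 meetings = 2,375 households per coupon group. Buyers: 0.40 × 2,375 = 950 and 0.06 × 2,375 = 142.5 (stated as 143). Total: 2,375 + 2,375 + 453 = 5,203. Buyers in the full sample: 950 + 143 + 453 = 1,546. Non-buyers: 5,203 − 1,546 = 3,657.

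**2. Order of events.** Meeting and lottery, agent visit, chance to buy, interview at two to seven weeks, follow-up at 12 and 24 months. Every answer used to predict purchase is given after the purchase decision.

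**3. Recall windows.** Minor incidents use a four-week recall. At two weeks after the meeting, 2/4 = 50% of that window falls after the meeting; at four weeks or more, all of it does. For the 12-month window used for major incidents, the share is 2/52 = 4% to 7/52 = 13%. So even factual predictors need an anchor, the four-week ones most.

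**4. What a shift alone would produce.** The size of any shift is not in the documents; the values below are assumptions, with no true selection.

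- *Binary item (such as expected facility use), 50% among non-buyers.* Odds ratio = [p/(1 − p)] / [0.5/0.5], where p is the share among buyers. Upward shift of 5 points: 0.55/0.45 = 1.22. 10 points: 0.60/0.40 = 1.50. 20 points: 0.70/0.30 = 2.33. A downward shift gives the reciprocals.
- *Continuous score, normal with equal variances.* A shift of d standard deviations (SD) gives an odds ratio of exp(d) per SD. The chance of a significant result (two-sided 5%, 1,546 against 3,657) is:

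| Shift (SD) | Odds ratio per SD | Design effect 1 | Design effect 2 | Design effect 3 |
|---|---|---|---|---|
| 0.05 | 1.05 | 38% | 21% | 16% |
| 0.1 | 1.11 | 91% | 65% | 48% |
| 0.2 | 1.22 | >99% | 99.7% | 97% |
| 0.3 | 1.35 | >99% | >99% | >99% |

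**5. What the lottery can show.** Coupons are random, so a large- versus small-coupon difference in an item is not selection. For a 50% item, the standard error of the arm difference is √(2 × 0.25/2,375) = 0.0145. Dividing by the take-up gap, 0.40 − 0.06 = 0.34, gives 0.043, or 4.3 points, for the implied purchase shift. The significance threshold is 1.96 × 4.3 = 8.4 points, at which power is only about 50%. For 80% power, (1.96 + 0.84) × 4.27 = about 12 points before clustering, or 12 × √2 = about 17 at an assumed design effect of 2. Power before clustering is about 65% for a 10-point shift and 22% for 5 points.

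Steps 4 and 5 together show an asymmetry. A 0.1 SD shift (5 points on a 50% item) is likely to appear as a significant predictor, yet the coupon comparison would usually miss it.

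**The case against.** The strongest reply is that selection does not rest on these items. Section 3 puts health status and prior utilization first. Objective 2 also compares buyers at different prices, and a purchase effect common to all buyers cancels there. SKY's own utilization records are a further source, and GRET quality surveys made before SKY arrived give facility quality free of this problem. All of this stands, and it limits the reach of the point. The cancellation, however, needs the shift to be equal among those who paid different prices, and it does not help the buyer versus non-buyer regression.

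Second, question wording is not shown, and Section 6.1 leaves the final indicators to pre-tests. Some attitude items could be phrased as of the meeting. That is possible, but the protocol ties only health level to the purchase date.

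A reader might make three stronger inferences that the documents do not support:

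- *That Objective 2 will report adverse selection where none exists.* No shift is documented, and the concern applies mainly to predicted need and expected use. Being covered does not obviously change perceived health risk, and no specific mechanism is documented for trust or willingness to try new products.
- *That the protocol concedes that joining raises perceived quality.* Expectations, in the Objective 3 passage, may well mean standards; higher standards would lower members' ratings.
- *That all attitude items should be dropped.* This would remove the risk-aversion measures that the positive-selection question needs.

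**Conclusion.** The point holds in a limited form. By the protocol's own schedule, the subjective predictors are collected after the outcome they are meant to explain, and the regression is to be read as impact. Gaps between buyers and non-buyers in perceived quality, predicted need, expected use and trust can therefore combine selection with effects of buying. Objective 2 has no safeguard, although Objective 3 recognises a related problem. A statistical analysis plan could change the interpretation but could not re-time the answers.

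The size and direction of the bias are unknown. The odds ratios of 1.22 to 2.33, and 1.05 to 1.35 per SD, rest on assumed shifts with no true selection, and the first set concerns an item like expected facility use rather than predicted health risk. Demographics, distance, the pre-SKY GRET surveys, and shocks or use dated before the meeting are much less exposed.

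**What to change.** 1. **Anchor the factual predictors.** Define illness, utilization and spending over a period ending at the village meeting, or record incident dates and count only those before it.
2. **Present two take-up models.** The main model uses pre-meeting facts. The second adds the attitude, expectation and risk-preference items, with results worded as associations with membership and not as impact.
3. **Add one table.** For each such item, give the large- versus small-coupon difference in the random sample, leaving out the oversampled buyers, with a village-clustered confidence interval, beside the buyer versus non-buyer gap. Describe it as an effect of the coupon offer, which may act through purchase or through the coupon itself. If it is scaled by the take-up gap, say that it then concerns households induced to buy by the coupon, so it is not directly comparable with the gap for all buyers. Do not treat a null result as clearing an item.

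**Cost.** Changes to recall wording and one table from data already planned. A four-week window ending at the meeting would begin 6 to 11 weeks before the interview (2 + 4 to 7 + 4), so recall of minor incidents would be poorer. Some determinants named in the objective would be reported only as associations. The interview need not move.

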SKY currently offers insurance to households in several rural districts in Takeo and Kandal provinces, and has recently expanded into the capital, Phnom Penh, targeting specific groups such as garment workers and market vendors. In December 2005, the program had 4,392 beneficiaries from 917 households, up over 160% from the previous year. Take-up of insurance ranges from 2% in regions where insurance has been only recently introduced to 12% in the longest served regions (SKY briefing note, 2005).

We will study SKY's 2007-8 expansion into additional districts in Takeo and Kandal provinces as well as parts of Kampot. We will evaluate the health and economic effects of the SKY program on households using a **randomized controlled trial.** The central methodological tool of this evaluation is randomized distribution of "Lucky Draw" coupons that will induce random variation in the likelihood of taking up insurance. Randomization allows estimation of the causal effects of health insurance as distinct from all other characteristics that vary across insured and non-insured households. We will also use in-depth interviews of a small group of households in selected villages to take a closer look at household behavior. Finally, interviews with households, health center staff, and SKY Member Facilitators will help to understand SKY's effects on health centers.

2. Objectives of the Study

The research has four objectives:

1. To estimate the causal effect of health insurance on households.

- Economic outcomes (e.g., medical spending; sales of productive assets; household debt and loans)

- Health outcomes (e.g., frequency and duration of illness; subjective self-health assessments; objective health measures)

- Health utilization (e.g., public health facility utilization; substitution to public facilities from private health centers and traditional medicine; preventative care utilization; timely utilization of curative care; self-medication)

2. To understand the determinants of take-up of health insurance; the extent of adverse and positive selection; the potential for risk-pooling.

- Household characteristics (e.g., wealth and income; age and sex composition; past health utilization; health status; perceptions of public facilities; expected utilization of public facilities; access to alternate sources of health financing; risk aversion)

- Public health facility characteristics (e.g., objective measures of quality; convenience of access)

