The randomization of premiums will provide a discount to some households. Of households that attend the village meeting, 20% of households, up to a maximum of 12 households per village, will win a coupon for 5-months free insurance in the first 6-month cycle, with the option to renew for a second 6-month cycle with a coupon for 3-months free. The remaining households in attendance at the meeting will be entitled to a coupon for a 1-month discount on insurance, which is the usual policy for the SKY program. SKY will be holding village meetings in Takeo, Kandal, and Kampot provinces over the course of the thirteen months from November 2007 to December 2008 (roughly the period during which the baseline survey will be administered). Table 1 shows an approximation of the distribution of the targeted sample across regions. The column "Total Meetings Held" indicates the number of village meetings SKY plans to hold in each district or province and "Total Lucky Draws" indicates the number of Lucky Draws held in the given district. The final column, "% of Villages Surveyed", indicates the approximate percentage of the sample that will come from each area. Note that we will hold Lucky Draws at most village meetings in 2008. We will only survey villages in which we hold a Lucky Draw.

				Total	Total	% of Villages	
				Meetings	Lucky	Surveyed	
				Held	Draws		
Takeo Province			128	128	51%		
Ang Roka village	s (older	villages)		32	32	13%	
Kirivong villages			48	48	19%		
Donkeo villages				48	48	19%	
Kandal Province	74	72	29%				
Koh Thom village	es			74	72	29%	
Kampot Province	50	50	20%				
Kampot villages				50	50	20%	
All Villages				252	250	100%	

Table 1: Targeted Regions

In addition to the randomized intervention, we will also be studying the effect of SKY on the quality and functioning of public health facilities. The fact that higher quality facilities are targeted by SKY means that there can be no valid control group in a longitudinal study, but we will use several methods to measure changes in health center quality over time that will allow us to gain some insight into the impact of SKY.

4. Sampling Strategy

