6.2. Economic Outcomes

If successful, SKY health insurance will have the following economic effects: (a) lower health-related spending; (b) lower health-related debt; (c) fewer cases of asset sales, savings and decreased investment; (d) less lost income due to illness. This section describes the indicators we will use to measure these economic impacts.

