2) health insurance = $\beta_0 + \alpha$ · high-value coupon for insurance + controls + u.

Here, "health insurance" is a variable equal to 1 if a household buys health insurance and 0 if a household does not buy health insurance, and "high-value coupon for nsurance" is a variable equal to 1 if a household wins a high-valued coupon for insurance, and 0 otherwise. The "controls" are any other characteristics that we believe

influence the purchase of health insurance. We can estimate α using a linear probability model (that is, OLS), although other functional forms are possible. We can use the estimated coefficients to predict p[^] ("p-hat"), the probability of having health insurance.

3) number of health center visits = controls + β_{2SLS} · p^A.

Now we can run a second-stage equation:*

As long as the coupon given in the lottery is uncorrelated with baseline health (or other determinants of health center visits), the two-stage least squares estimate β_{2SLS} will be an unbiased estimate of the true effect of health insurance on health center visits. This procedure is called two-stage least

squares or instrumental variables techniques, with the coupon value as the instrument.⁵

It might be simpler to think of the analysis in 2 pieces. We can run a non-causal reduced form equation (where Δ = change in a variable):

4) number of health center visits = controls + γ * high-value coupon for insurance.

Now the coefficient we care about is β , and can be estimated by:

 $\beta^{A} = \Delta$ health center visits / Δ insurance status

= (Δ health center visits/ Δ coupon value) / (Δ (insurance status) / Δ coupon value)

$$= \gamma^{\prime} / \alpha^{\prime}$$
.

That is, the ratio of the coefficient from the reduced form equation (4) (how coupons affect health center visits) to the coefficient from the first stage in equation (2) (how coupons affect insurance uptake) can tell us how insurance affects health center visits. Intuitively, assume coupons are distributed in random lotteries, and having a valuable one leads to a 50 percentage points higher probability of buying insurance. Moreover, assume households with coupon winners also have 1.5 extra health center visits per year (on average). Then it appears the causal link between buying insurance and visiting health centers = 1.5 more health center visits / 50% more insurance = 3 more health center visits for households with (exogenously) higher insurance.

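### For money outcomes the large coupon also acts through the lower premium paid, so the IV estimate is not the effect of insurance alone, and it describes insurance at the coupon price, not SKY as usually sold

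*Protocol*

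**What the plan says.** Section 3 describes the large coupon as "5-months free insurance in the first 6-month cycle, with the option to renew for a second 6-month cycle with a coupon for 3-months free". Other meeting attenders receive a "coupon for a 1-month discount on insurance, which is the usual policy for the SKY program". The notes to Table 2 give the expected uptake: "we assume 40% of large coupon winners purchase SKY and 6% of small coupon winners purchase SKY".

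Section 6.1 makes the large coupon an instrument for taking up insurance. In part a of the Statistical Appendix, the treatment variable is a 0/1 indicator of purchase, so the price paid does not enter the model. The appendix opens by aiming at health care utilization or another outcome. It claims an unbiased estimate of the true effect of insurance under a condition beginning "As long as the coupon given in the lottery is uncorrelated with baseline health (or other determinants of health center visits". Its mathematical note asks that the instrument be unrelated to other factors affecting health care utilization.

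The introduction sets the aim: "We will evaluate the health and economic effects of the SKY program on households using a" randomized trial. The benefits that Section 6.2 expects include "b) lower health-related debt; (c) fewer cases of asset sales, savings and decreased investment".

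**The concern.** An instrument must be independent of the outcome's other determinants, which the lottery secures at baseline. It must also affect the outcome only through the treatment. The appendix expresses the second requirement only for health center visits and utilization. It never asks whether the requirement holds for economic outcomes, where it is least plausible because the instrument is a price cut.

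Two consequences follow, and they differ in kind.

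- Households that would buy under either coupon hold the same insurance in both arms but pay less if they win. Any effect of that saving on debt or asset sales is divided by the first stage and reported as an effect of insurance. This is a failure of exclusion.
- Households that buy only because of the large coupon are insured at a reduced price. Their estimate is sound for that price. However, the introduction promises the effects of the SKY program, and the text on Objective 4 offers the results to governments and aid organizations weighing voluntary insurance. Those readers will take the estimate as applying at SKY's normal price.

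Wherever premium money reaches the outcome, both work in SKY's favour.

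**Working it through.** **Inputs**

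- Large coupon: 5 free months of the first 6, plus 3 of the next 6 on renewal (Section 3).
- Small coupon: 1 free month, the usual terms (Section 3).
- Take-up: 0.40 and 0.06 (notes to Table 2).
- Renewal share r: not given, so 0 to 1 is used.
- Premium: not given, so results are in months of premium.

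**The plan's own ratio.** The appendix computes 1.5/0.5 = 3 extra visits. From the cells of Table 4, (2.5 − 1.03)/0.5 = 2.94, which agrees within rounding. The same ratio is now applied to months of premium paid.

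**Groups.** Assume that no household buys with the small coupon but declines with the large one. Then 0.06 always buy, 0.40 − 0.06 = 0.34 are induced to buy, and 0.60 never buy. Always-buyers per induced buyer: 0.06/0.34 = 0.176.

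**Price difference between arms for a buyer.** (5 + 3r) − 1 = 4 + 3r months. This assumes the same renewal share in every buyer group and no free month for small-coupon buyers in the second cycle.

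**Months paid.** A large-coupon buyer pays 1 + 3r and a buyer on usual terms pays 5 + 6r. The IV estimate of premium paid per induced buyer is

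[0.40 × (1 + 3r) − 0.06 × (5 + 6r)] / 0.34.

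| Renewal r | Induced buyer pays | Usual terms | IV estimate of premium paid | Always-buyer term, 0.176 × (4 + 3r) | Price gap, 4 + 3r |
|---|---|---|---|---|---|
| 0 | 1 | 5 | 0.10/0.34 = 0.29 | 0.71 | 4 |
| 0.5 | 2.5 | 8 | 0.52/0.34 = 1.53 | 0.97 | 5.5 |
| 1 | 4 | 11 | 0.94/0.34 = 2.76 | 1.24 | 7 |

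**Reading the table.** With full renewal an induced buyer really pays 4 months, but the ratio registers 2.76. The missing 4 − 2.76 = 1.24 months is the always-buyers' saving credited to insurance. With no renewal it is 1 − 0.29 = 0.71. The rest of the distance from usual terms (11 − 4 = 7, or 5 − 1 = 4) is the lower price that induced buyers face.

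**Alternative assumption.** If small-coupon buyers also got a free month in the second cycle, the full-renewal price gap would be 6 and the always-buyer term 6 × 0.176 = 1.06.

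**Effect of the proposed adjustment.** Charging large-coupon buyers their free months beyond the usual one puts both arms on usual terms. With full renewal the ratio becomes (0.40 × 11 − 0.06 × 11)/0.34 = 11, and with none (0.40 × 5 − 0.06 × 5)/0.34 = 5. These match usual terms, so at one-for-one pass-through the adjustment removes both components.

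**The case against.** The appendix does not rest on random drawing alone. Its condition reaches other determinants of visits, and it later rules out anything else that predicts health center use. That is an exclusion-type condition. It also confines the estimate to attenders induced to buy, and it labels the intention-to-treat contrast as the effect of the coupon. A sensitivity column could also sit in an SAP that is not shown.

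Much of this is right, but it leaves the point standing. The condition is illustrated on one outcome and never reconsidered for money outcomes, to which the method is explicitly extended. The limit on the estimand says whose effect is estimated, not at what price. What needs correcting is the identification claim, and that is in the protocol.

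Several stronger readings are tempting and are not supported:

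- **That the full 4.71 to 8.24 months (both components together) is coupon cash wrongly credited to insurance.** Without the coupon, an induced buyer has no insurance and pays no premium. With it, that household pays 1 to 4 months and receives no windfall. Only the always-buyer term is misattributed; the rest is distance from a different estimand.
- **That large-coupon buyers simply get 8 of 12 months free.** The last 3 months depend on renewal, and the text offers this only "with the option to renew for a second 6-month cycle". No renewal rate is given.
- **That the economic effect could reverse at SKY's usual price.** The protocol gives neither a premium nor an expected economic effect, so this is conjecture.
- **That all the economic indicators are equally exposed.** In Sections 6.2.2 and 6.2.3, the savings indicator and the health-specific debt, loan and asset-sale items concern paying for health care or health expenses. Premium money reaches them mainly indirectly.

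**Conclusion.** The point holds in limited form. For money outcomes, mainly total outstanding debt and any asset sale, the appendix's claim to a causal effect of insurance needs an exclusion condition that the coupon does not meet. The resulting misattribution is 0.71 to 1.24 months of premium per induced buyer. Separately, the estimate describes insurance at the coupon price and omits 4 to 7 months of premium relative to usual terms.

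These figures rest on the protocol's assumed take-up of 40% and 6%, equal renewal among buyer groups, and no household deterred from buying by the large coupon. They measure premium money, not the bias in an outcome: with no pass-through to debt or asset sales the bias is zero, and the money value cannot be computed. The 12-month round is most exposed. The coupons described cover at most two 6-month cycles, so the 24-month round can only carry their value over.

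This affects what may be concluded about SKY's economic benefit and should be put right. Utilization and health outcomes need no change.

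**What to change.** 1. In part a of the Statistical Appendix, state that the coupon must act on the outcome only through insurance, and that this fails for money outcomes because the coupon also lowers the premium paid.
2. Label all economic IV estimates as effects of insurance at the subsidised price among those induced to buy. For yes/no indicators such as any asset sale, the label is the whole remedy, since a premium amount cannot be charged to them.
3. For money-valued outcomes such as outstanding debt, report beside the planned estimate a version that charges each buying household the value of its free months beyond SKY's usual one (months × premium). The text on Objective 2 already plans to use SKY membership data; the premium would have to be added. Charging all free months would be wrong, because it would price insurance at 12 months instead of the usual 11.
4. Describe the pair as a sensitivity range for pass-through of 0 to 1, not as bounds. Section 6.2.2 considers debt at more than 8% interest per month, so pass-through could exceed one.

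The cost is one derived variable, one extra column per money-valued outcome and a few sentences. The downside is a less favourable economic result, given as a range.
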